2. INTRODUCTION

2.1. Background

2.1.1. Tenosynovial Giant Cell Tumor (TGCT)

Tenosynovial giant cell tumor (TGCT) is a rare, nonmalignant neoplasm of the synovium, bursae, or tendon sheaths that is driven by overexpression of colony-stimulating factor-1 (CSF-1) often afflicting adults under 40 years of age. Annual TGCT incidence is estimated to be 43 cases per one million individuals, of which approximately 10% are of the diffuse subtype. Surgical resection, when feasible, is the standard treatment for TGCT; however, recurrence of the diffuse subtype is particularly common. Repeated surgeries often result in increasing morbidity and functional limitations of the affected joints. The diffuse disease often has more extensive involvement and a poorer likelihood of a successful cure with surgery, and therefore often may not be amenable to surgical resection due to the risk of morbidity or high risk of recurrence in diffuse disease. Systemic therapies targeting CSF-1 activity are being evaluated for the treatment of TGCT.

2.1.2. Pexidartinib (PLX3397)

Pexidartinib is an oral small-molecule tyrosine kinase inhibitor that targets 3 kinases: CSF-1 receptor ([CSF-1R] or feline McDonough sarcoma [FMS] kinase); proto-oncogene receptor tyrosine kinase (c-Kit), and FMS-like tyrosine kinase 3. TURALIO™ (Pexidartinib) was approved, 02 Aug 2019, by the United States (US) Food and Drug Administration (FDA) for the treatment of symptomatic TGCT associated with severe morbidity or functional limitations and not amenable to improvement with surgery. Pexidartinib is the first systemic therapy to show a robust tumor response in TGCT with improved patient symptoms and functional outcomes; cholestatic hepatotoxicity has been identified as a risk. It was approved with a boxed warning for hepatotoxicity and is available only through a restricted program called the TURALIO Risk Evaluation and Mitigation Strategy (REMS) program.

The approval was based on the durable overall response rate (ORR) observed in the Phase 3 study PLX108-10 (ENLIVEN) which provided compelling evidence of its effectiveness for the treatment of subjects with TGCT. In the ENLIVEN study, an international, multicenter, randomized (1:1), double-blind, placebo-controlled study, 120 subjects with TGCT not amenable to surgical resection and treated with pexidartinib had a robust tumor response rate versus placebo at Week 25 by Response Evaluation Criteria in Solid Tumors (RECIST) Version 1.1 (39% vs 0%; P<0.0001) and by tumor volume score (TVS) (56% vs 0%; P<0.0001). Further evidence of tumor response and clinical improvements are noted in the TGCT extension cohort of Study PLX108-01, as well as the longer-term data from the ENLIVEN study.

The safety data showed serious adverse events (SAEs) occurred in 13% (8/61) of patients in the pexidartinib group and 2% (1/59) of patients in the placebo group. The most frequent pexidartinib-associated treatment-emergent adverse events (TEAEs) were hair color changes, fatigue, aspartate aminotransferase (AST) increase, nausea, alanine aminotransferase (ALT) increase, and dysgeusia. Pexidartinib was associated with 2 types of hepatic adverse reactions. The first was a dose-dependent, generally low-grade aminotransferase elevation related to the

CSF-1R inhibition mechanism of action. These elevations are primarily observed during the first 8 weeks of treatment. The second hepatic adverse reaction, mixed or cholestatic hepatotoxicity, which while rarely serious can be life-threatening, also generally appeared in the first 8 weeks of treatment, however, is uncommon and idiosyncratic in nature.

As noted, long-term follow-up showed further increases in tumor response with continued pexidartinib treatment. For long-term pooled efficacy and safety, 130 patients in ENLIVEN and PLX108-01 received pexidartinib; 47% (61) patients remained on treatment at data cut-off.

Median follow-up from first dose to data cutoff was 23 months (range, 16, 67); median treatment duration was 17 months (range, 1, 60+). Four percent (5) patients discontinued pexidartinib due to progressive disease (PD). Pooled RECIST v1.1-based best overall response (BOR) was 54%, with increased BOR from longer treatment. The safety profile was consistent with earlier reports, with no new safety signals.

Currently, besides the ENLIVEN and PLX108-01 studies, there are 2 additional Phase 1/2 studies (Study PL3397-A-A103 and Study PL3397-A-U126) that are ongoing. The objectives of these 4 pexidartinib studies in TGCT have been met and the investigational sites are to be closed. Eligible subjects from these studies will be included in the subject population for this study.

Refer to the *Pexidartinib Investigator's Brochure (IB)* for additional details and information.

2.2. Study Rationale

Over time, with daily treatment, many patients on long-term use of pexidartinib in these studies achieved significant tumor responses. In the ENLIVEN study, with the 90-day post-treatment observation period, no cases of rapid tumor regrowth were observed, suggesting that quarterly follow-ups are of adequate frequency to identify any patients, who need to re-initiate their treatment. However, beyond the 3-month post-treatment follow-up in ENLIVEN, there are no data to fully understand the impact of discontinuing pexidartinib treatment in patients with stable and/or residual disease. And, with slow-growing disease like TGCT, 3 months is not sufficient to determine the time when the treatment needs to be restarted. Feasibility of intermittent on-off dosing remains an open medical question.

Patients with TGCT diagnosed early in their lives face potentially several decades of daily treatment. In the real-world setting, subjects and Investigators are faced with decisions surrounding patients' activities of daily living and treatment with pexidartinib for TGCT. Further data are necessary to fully understand the safe and effective discontinuation and re-treatment with pexidartinib therapy in this patient population.

The purpose of this Phase 4 multicenter study in subjects with TGCT previously treated with pexidartinib are two-fold. At the Screening visit/time of consent, the Investigators and subjects are provided the choice to either continue treatment with pexidartinib or discontinue treatment with the possibility of re-initiating pexidartinib treatment at a later time. Findings from this study will provide important prospective discontinuation and re-treatment data with pexidartinib in previously treated subjects with residual disease.

Ultimately, this study will contribute meaningful information to the body of research on pexidartinib treatment for patients with TGCT and the safe and effective discontinuation and re-treatment with pexidartinib therapy.

2.3. Benefit and Risk Assessment

As noted, in the Pexidartinib Clinical Development Program, pexidartinib has demonstrated statistically significant and clinically meaningful efficacy. The efficacy data from the ENLIVEN study provide evidence of its effectiveness for the treatment of subjects with TGCT. Further evidence of tumor response and clinical improvements are noted in the TGCT extension cohort of the PLX108-01, as well as the longer-term data from the ENLIVEN study.⁶ The benefits for subjects treated with pexidartinib in these studies is expected to continue to be observed in this study.

Pexidartinib can cause hepatic adverse reactions, including aminotransferase abnormalities or mixed or cholestatic hepatotoxicity that may be fatal. Hepatotoxicity is an important adverse drug reaction (ADR). Serious and prolonged hepatotoxicity with ductopenia and/or cholestasis has been observed in subjects treated with pexidartinib. Cases of cholestasis have been observed in the first 8 weeks and have generally resolved with treatment discontinuation, but in some cases have been severe, with a protracted course requiring, in 1 case, transplantation. The mechanism of cholestatic hepatotoxicity is unknown, and its occurrence cannot be predicted.

Also, guidance on protocol-defined dose reductions, discontinuation of pexidartinib, increased frequency of laboratory monitoring, and reporting of findings have been established. After re-initiating treatment with pexidartinib the liver function tests AST, ALT, total bilirubin, direct bilirubin, alkaline phosphatase (ALP), and gamma-glutamyl transferase (GGT) will be monitored weekly for the first 8 weeks, every 2 weeks for 1 month, and every 3 months thereafter. The dose of pexidartinib will be reduced, withheld or permanently discontinued based on the severity of hepatotoxicity. Re-challenge with pexidartinib is not to be attempted without prior discussion with the Sponsor's Medical Monitor.

Re-challenges with a reduced dose of pexidartinib may result in a recurrence of increased serum transaminases, bilirubin, or ALP. The mixed or cholestatic hepatotoxicity is idiosyncratic and may therefore recur with re-challenge. Therefore, liver function tests are to be monitored weekly for the first 2 months after re-challenge, then every 2 weeks for 1 month, and then once every 3 months or more frequently as directed by the Investigator. Both the Investigator and subjects will be educated by the Sponsor on the eligibility criteria, benefits/risks of pexidartinib, necessary liver monitoring testing and guidance on dose reduction, and discontinuation.

In addition, administration with food increases pexidartinib exposure by 100% and may increase the risk of hepatotoxicity. Therefore, Investigators and subjects are instructed that pexidartinib administration is to be on an empty stomach, at least 1 hour before or 2 hours after a meal or snack. Investigators and subjects will also be instructed to avoid concomitant use of pexidartinib with strong cytochrome P450 (CYP)3A inhibitors or uridine 5'-diphospho-glucuronosyltransferase (UGT) inhibitors during the study.

Refer to the *Pexidartinib IB* for additional details and information.

3. OBJECTIVES, OUTCOME MEASURES, AND ENDPOINTS

The objectives, definitions of associated endpoints, as well as applicable outcome measures are described in [Table 3.1](#) and [Table 3.2](#). Further requirements for the endpoint analyses and censoring rules, where applicable, can be found in [Section 9.5.1](#), [Section 9.5.2](#), and [Section 9.5.3](#).

Table 3.1: Description of Objectives, Outcome Measures, and Endpoints (Treatment-Free/Re-Treatment Cohort)

Period	Objectives	Outcome Measure	Endpoints	Category
Primary Objective				
Overall	Proportion of subjects who remain treatment-free	
Title: Proportion of treatment-free subjects at 12 months and 24 months
 
Description: Proportion of subjects who remain treatment-free at Month 12 and Month 24
 
Time frame: 24 months after last subject enrolled in the Cohort
	Proportion of subjects who remain treatment-free at Month 12 and Month 24	Efficacy
Secondary Objectives				
Treatment-Free period	Change from Baseline in Patient Reported Outcomes (PROs)	
Title: Change from Baseline in PROs
 
Description: Change from Baseline in PROs (PROMIS PF, EQ-5D-5L)
 
Time frame: 24 months after last subject enrolled in the Cohort
	Mean change from Baseline* for PROMIS PF and EQ-5D-5L quarterly for the treatment-free and Re-Treatment periods. *Note: Baseline is Screening values.	Efficacy
	Safety	
Title: Number of subjects with AE during the Treatment-Free period*
 
Description: Total number of subjects in the safety analysis set with any AE collected between Screening and start of re-treatment or final database lock (whichever occurs first)
 
Time frame: 24 months after last subject enrolled in the Cohort
 
*Note: Listed as a secondary objective but is a primary outcome measure.
	Incidence of AEs and SAEs, ECGs, and laboratory assessments	Safety
Re-Treatment period	Tumor Assessment	
Title: Tumor assessment
 
Description: Investigator evaluation of tumor
 
Time frame: 24 months after last subject enrolled in the Cohort
	Qualitative assessment of the tumor	Efficacy
	Change from Baseline in Patient Reported Outcomes (PROs)	
Title: Change from Baseline in PROs
 
Description: Change from Baseline in PROs (PROMIS PF, EQ-5D-5L)
 
Time frame: 24 months after last subject enrolled in the Cohort
	Mean change from Baseline* for PROMIS PF and EQ-5D-5L quarterly for the Re-Treatment periods. *Note: Baseline is reinitiated with subject entering Re-Treatment period.	Efficacy
	Safety	
Title: Number of subjects with AE during the Re-Treatment period*
	Incidence of TEAEs and SAEs, ECGs, and laboratory assessments	Safety

Period	Objectives	Outcome Measure	Endpoints	Category
		
Description: Total number of subjects in the safety analysis set with any AE collected between first re-treatment dose and final database lock
 
Time frame: 24 months after last subject enrolled in the Cohort
 
*Note: Listed as a secondary objective but is a primary outcome measure.
		

AE = adverse event; EQ-5D-5L = EuroQol-Five Dimension Five Level Scale; PRO = Patient-Reported Outcomes ; PROMIS PF = Patient-Reported Outcomes Measurement Information System – Physical Function; SAE = serious adverse event; TEAE = treatment-emergent adverse event

Table 3.2: Description of Objectives, Outcome Measures, and Endpoints (Treatment Continuation Cohort)

Objectives	Outcome Measure	Endpoints	Category
Primary Objective			
None			
Secondary Objectives			
Tumor Assessment	
Title: Tumor assessment
 
Description: Investigator evaluation of tumor
 
Time frame: 24 months after last subject enrolled in the Cohort
	Qualitative assessment of the tumor	Efficacy
Change from Baseline in PROs	
Title: Change from Baseline in PROs
 
Description: Change from Baseline in PROs (PROMIS PF, EQ-5D-5L)
 
Time frame: 24 months after last subject enrolled in the Cohort
	Mean change from Baseline* for PROMIS PF and EQ-5D-5L at quarterly assessments. 
*Note: Baseline is Screening values.
	Efficacy
Safety	
Title: Number of subjects with TEAE during the study*
 
Description: Total number of subjects in the safety analysis set with any AE collected between first dose and final database lock
 
Time frame: 24 months after last subject enrolled in the Cohort
 
*Note: Listed as a secondary objective but is a primary outcome measure.
	Incidence of TEAEs and SAEs, ECGs, and laboratory assessments	Safety

AE = adverse event; ECG = electrocardiogram; EQ-5D-5L = EuroQol-Five Dimension Five Level Scale; PRO = Patient-Reported Outcomes ; PROMIS PF = Patient-Reported Outcomes Measurement Information System – Physical Function; SAE = serious adverse event; TEAE = treatment-emergent adverse event

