1. Subjects in the **Treatment Continuation Cohort** will remain on their current dosage of pexidartinib and undergo study assessments at 3-month intervals for a maximum of 24 months.
2. Subjects from the **Treatment-Free/Re-Treatment Cohort** who enter the Treatment-Free period will undergo study assessments 1 month after enrollment, 3 months after enrollment, and then at 3-month intervals for 24 months or until re-treatment with pexidartinib.

Subjects from the **Treatment-Free/Re-Treatment Cohort** who enter the Re-Treatment period will undergo efficacy and safety study assessments at 3-month intervals until the total time within this Cohort reaches 24 months; a new Baseline will be established upon entry into re-treatment. Liver safety assessments will follow a separate schedule.

All subjects will remain on study for a maximum of 24 months. The study will end with the completion of the last subject's 30-day safety follow-up or with their withdrawal from the study. A post-trial access plan, delineating options for access to pexidartinib, will be available for subjects after completing their study participation if the subject is benefiting from the study drug.

Key Eligibility Criteria

Subjects must meet the following key inclusion/exclusion criteria:

Inclusion Criteria:

1. Currently enrolled and have not discontinued pexidartinib treatment in one of the following studies: Study PLX108-10 (ENLIVEN), Study PLX108-01, Study PL3397-A-A103, or Study PL3397-A-U126.
2. Willing and able to complete the PROMIS Physical Function Scale and EQ-5D-5L throughout the study.
3. Willing and able to provide written informed consent prior to any study-related procedures and to comply with all study requirements.
4. Females of reproductive potential must have a negative urine pregnancy test at Screening/Baseline (to be confirmed by a serum pregnancy test taken on the last-treatment visit of their prior study) and should be advised to use an effective,

non-hormonal method of contraception during treatment with pexidartinib and for 1 month after the last dose. Males with female partners of reproductive potential should be advised to use an effective method of contraception during treatment with pexidartinib and for 1 month after the last dose. Female partners of male patients should concurrently use effective contraceptive methods (hormonal or non-hormonal).

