4.1.1. Design Overview

Subjects in the 4 ongoing TGCT studies will be screened at the "End-of-Treatment (EOT) visit" (i.e., the visit at which they receive their final dose of pexidartinib) of their previous study, at which time they can elect to enroll in the PL3397-A-U4003 study in 1 of 2 cohorts – the **Treatment Continuation Cohort** (where their existing pexidartinib treatment will continue uninterrupted) or **Treatment-Free/ Re-Treatment Cohort** (where they will discontinue pexidartinib treatment with the possibility to re-initiate treatment over the course of the study). Subjects who elect to not enroll in the PL3397-A-U4003 study will remain in their current study and complete their respective End-of-Study activities.

Subjects who elect to enroll in PL3397-A-U4003 will sign an institutional review board (IRB)/independent ethics committee (IEC)-approved informed consent form (ICF). By signing the ICF, subjects will permit acquisition and data transfer of any data collected in their precursor study, including, but not limited to, medical and surgical history, and prior medications. The assessments performed during the preceding study's End-of-Treatment visit will serve as the Baseline measurements for the PL3397-A-U4003 study.

Eligible subject who choose to continue pexidartinib treatment in the **Treatment Continuation Cohort** will remain on their current dosage regimen of pexidartinib and undergo clinical assessments at 3-month intervals for the duration of the study.

Subjects who choose to discontinue pexidartinib will be enrolled in the Treatment-Free period of the **Treatment-Free/Re-Treatment Cohort**. These subjects will stop pexidartinib dosing at entry into PL3397-A-U4003 (i.e., after their final dose at the preceding study's EOT visit). Subjects will undergo clinical assessments 1 month after enrollment, 3 months after enrollment, and then at 3-month intervals. Subjects will remain treatment-free until retreated with pexidartinib, based on the Investigator and/or subject's discretion. Considerations are given to tumor response, subjective and/or functional measures, and safety parameters in the decision-making process. The rationale for discontinuation and re-treatment with pexidartinib will be recorded accordingly.

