9.4. Population for Analysis Sets

Analysis Sets

- The Safety Analysis Set will include all subjects who entered this study. Subjects will be analyzed according to their cohort (**Treatment-Free/Re-Treatment Cohort; Treatment Continuation Cohort**).
- The Full Analysis Set (FAS) for the **Treatment-Free/Re-Treatment Cohort** will include all subjects who entered the Treatment-Free/Re-Treatment Cohort. This data set will be the primary population for the primary endpoint.
- The Full Analysis Set (FAS) for the **Treatment Continuation Cohort** will include all subjects who entered the Treatment Continuation Cohort.
- The Evaluable Analysis Set (EAS) will include all subjects who entered the study with Baseline measure and at least 1 post-baseline measures available. The data set will be used for PRO measures.
- The Re-Treatment Analysis Set (RAS) will include all subjects who received at least 1 dose of pexidartinib in the **Treatment-Free/Re-Treatment Cohort** after stopping pexidartinib. The data will be used for both efficacy and safety analyses for re-treated subjects in the **Treatment-Free/Re-Treatment Cohort**.

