9.5.1.1. Primary Efficacy Analyses

The primary endpoint in this study is the proportion of subjects who remain treatment-free at Month 12 and Month 24 after entering the Treatment-Free period in the **Treatment-Free/Re-Treatment Cohort**. The primary efficacy analysis will be based on the data from the FAS.

Kaplan-Meier methods will be used to estimate the proportion of subjects who remain treatment-free at Month 12 and Month 24. Estimate of the proportion will be provided with its 95% confidence interval (CI) using Greenwood's formula.

The subjects who resume pexidartinib treatment or died will be considered as an event. The subjects who take subsequent systemic therapy or undergo surgery for the treatment of TGCT will also be counted as an event. The subjects who withdraw consent or lost to follow up will be censored at the last contact date.

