9.5.1.2. Secondary Efficacy Analyses

The PRO measures will be summarized descriptively over time along with its 95% CI by each cohort. The mean change from Baseline for these measures will also be reported over time along with its 95% CI by each cohort. The analysis will be conducted in the Evaluable Analysis Set (EAS).

Similar analyses will be conducted in the Re-treatment Analysis Set subjects (RAS). In this analysis, the Baseline measure of the retreated subjects is defined as the latest measure prior to or on the date of re-treatment of pexidartinib.

Qualitative assessments of the tumor will be summarized descriptively for pexidartinib re-treated subjects in the **Treatment-Free/Re-Treatment Cohort** and for all subjects in the **Treatment Continuation Cohort**.

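### TGCT surgery or another systemic TGCT drug ends treatment-free status in the primary endpoint but does not close the Treatment-Free adverse-event window, and the PRO summary for that period is cut at neither that date nor pexidartinib restart

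*Combined protocol and SAP*

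**What the plan says.** **Primary endpoint (Section 9.5.1.1).** "Kaplan-Meier methods will be used to estimate the proportion of subjects who remain treatment-free at Month 12 and Month 24". Two sentences define the event: "The subjects who resume pexidartinib treatment or died will be considered as an event", and "The subjects who take subsequent systemic therapy or undergo surgery for the treatment of TGCT will also be counted as an event". Withdrawal of consent and loss to follow-up are censored at last contact.

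**Treatment-Free AE count (Table 3.1, repeated in the synopsis).** The outcome measure is the number of subjects with "any AE collected between Screening and start of re-treatment or final database lock (whichever occurs first". A note says that it is listed under secondary objectives but is a primary outcome measure. Section 9.5.2 assigns each AE to the study period in which it began.

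**What re-treatment means.** Section 4.1.1: "Subjects will remain treatment-free until retreated with pexidartinib". In Section 9.4 the Re-Treatment Analysis Set "will include all subjects who received at least 1 dose of pexidartinib" after stopping it. In the synopsis, Treatment-Free visits run at 1 and 3 months, "then at 3-month intervals for 24 months or until re-treatment with pexidartinib".

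**PROs.** The PRO row under the Treatment-Free period in Table 3.1 covers that period and the Re-Treatment period together, measured from the Screening baseline. Section 9.5.1.2, on the Evaluable Analysis Set: "The mean change from Baseline for these measures will also be reported over time along with its 95% CI by each cohort". A separate analysis of re-treated subjects uses a new baseline.

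**The concern.** One term has two end dates. For the primary endpoint, a subject stops being treatment-free on the day of TGCT surgery or the first dose of another systemic TGCT drug. For AE counting, the same subject stays in the Treatment-Free period until pexidartinib restart or database lock.

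The case is foreseeable: Section 2.1.1 describes resection, where feasible, as standard treatment, and Section 9.5.1.1 provides for both surgery and other systemic therapy.

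The study is meant to inform safe and effective discontinuation (Section 2.2). Surgical complications or toxicity of another drug can enter a headline AE count that readers will take as experience off all TGCT treatment. Functional change after surgery, and after pexidartinib restart, can enter the PRO means that sit under the Treatment-Free heading. The primary and secondary results would then describe different stretches of time in the same subjects, with nothing in the tables to show it.

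**Working it through.** The plan states no sample size, event rate or AE rate, so there is no figure to reproduce. The check is a comparison of rules, followed by an illustration of scale.

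**Step 1: the rules side by side.**

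| What happens to the subject | Primary endpoint (9.5.1.1) | Treatment-Free AE window (Table 3.1) | By-cohort PRO summary (Table 3.1, 9.5.1.2) |
|---|---|---|---|
| Pexidartinib restart | Event | Closes | Continues |
| Other systemic TGCT therapy, no restart | Event | Stays open | Continues |
| TGCT surgery, no restart | Event | Stays open | Continues |
| Death | Event | No further data | No further data |
| Database lock | n/a | Closes | n/a |

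The AE mismatch lies in the second and third rows. The PRO gap is wider, because the first row is affected too.

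**Step 2: follow one subject.** The subject has TGCT surgery just after the Month 6 visit, does not restart and stays in the study. The subject is an event before Month 12. A complication that starts before the Month 9 visit falls in the Treatment-Free period under Section 9.5.2 and, if recorded, counts as a Treatment-Free AE. The Month 9 and later PROs enter the cohort mean with no marker.

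**Step 3: look for a rule that closes the gap.**
- Section 3 refers to Sections 9.5.1 to 9.5.3 for further endpoint and censoring rules. Section 9.5.1.2 gives none for PROs, and Section 9.5.3 plans no other analyses.
- Section 7 says that it does not describe subjects in the Treatment-Free period.
- Section 4.1.2 foresees only re-treatment or remaining treatment-free.
- Table 1.2, note a, runs visits to the Re-Treatment period or end of study.

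None ends the period, or requires withdrawal, at surgery or other therapy.

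**Step 4: possible size of the AE effect (all inputs assumed).** Let f be the proportion of the cohort with other TGCT therapy and no restart, p the proportion who would have an AE in the window anyway, and q the chance that a subject without such an AE has one recorded after the other therapy. The rise in the percentage with any AE is f × (1 − p) × q. With q = 1, the upper end:

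| f | p = 40% | p = 70% | p = 80% | p = 95% |
|---|---|---|---|---|
| 5% | 3.0 | 1.5 | 1.0 | 0.25 |
| 10% | 6.0 | 3.0 | 2.0 | 0.5 |

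Entries are percentage points. With q = 0.5 each halves.

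**Step 5: share of follow-up affected (all inputs assumed).** Take constant, independent hazards, with 24-month risks R of restart and O of other therapy. Each hazard is −ln(1 − risk)/24, and mean time in the window is (1 − e^(−24λ))/λ. For R = 40% and O = 10%:
- window to restart: λ = 0.021284, mean = 0.40/0.021284 = 18.79 months;
- window to restart or other therapy: λ = 0.025674, mean = 0.46/0.025674 = 17.92 months;
- share of the window after other therapy: about 4.7%.

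Over R = 20-60% and O = 5-10%, the share is 2.1-4.9%.

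No size is given for PROs. The plan gives no numbers per visit, no standard deviation and no expected change after surgery, and it does not define the not-restarted subset that such a calculation would need.

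**The case against.** **These may be two constructs rather than a contradiction.** The primary endpoint is a composite outcome. The Treatment-Free period is an operational period off pexidartinib. Counting every AE until restart is a legitimate treatment-policy summary, and surgery or another drug may itself follow from stopping pexidartinib. Cutting the count at that date and reporting nothing else could make discontinuation look safer than it is. This stands, and it is why the full count should be kept.

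**PRO rules may come in the SAP.** Section 9.5.1 defers detailed censoring rules for applicable secondary efficacy endpoints to the SAP. That leaves room to settle PROs there, though the text reviewed contains no such rule. The deferral covers efficacy; the AE window is already written in Table 3.1.

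**The AE effect may be small.** Section 8.4.1, read literally, stops recording non-serious AEs 30 days after the last dose, which conflicts with Tables 1.2 and 3.1. Section 10.5.1 excludes procedures themselves, and Section 8.4.1 excludes TGCT worsening. An investigator could withdraw such subjects, and pexidartinib can be restarted instead. The study is descriptive, and AE listings with relationship to study drug are planned. All this limits the size but does not remove the mismatch.

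**Stronger readings that the documents do not support.**
- A reader might infer that the Treatment-Free PRO summary ends at restart and so credits surgical benefit purely to being off drug. The summary is by cohort over both periods and already includes re-treated subjects.
- A reader might infer that the Re-Treatment period and the Continuation Cohort need the same cut-off. The mismatch quoted here does not arise there. For subjects on treatment who end participation early without radiologic progression, Section 4.1.1 already places a final MRI no later than any new TGCT therapy.
- Shifts above 6 points need assumptions such as 20% having other therapy, for which the documents give no basis.

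**Conclusion.** The concern holds as a gap in definition and reporting. By the stated rules, AEs that start after TGCT surgery or another systemic TGCT drug count as Treatment-Free AEs in subjects who have already had the primary event. The PRO summary under the same heading separates neither post-other-therapy nor re-treated assessments.

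The effect arises only if such subjects remain in the study without restarting, which no rule prevents. Its size cannot be derived from the documents. Under the Step 4 assumptions with every affected subject having a later AE, the AE percentage moves by about 0.25-6 points; it would be less with incomplete recording or early withdrawal. The primary Kaplan-Meier estimate is not affected. The point merits correction because the AE count is designated a primary outcome measure and the repair is cheap.

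**What to change.** Change the analysis text in Table 3.1, the synopsis and Sections 9.5.1.2 and 9.5.2. Visits, data collection and clinical management stay as they are.

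1. Keep the count of subjects with any AE from Screening to re-treatment or database lock.
2. Add a split at the Section 9.5.1.1 event date. One row gives AEs that start up to the earliest of pexidartinib restart, other systemic TGCT therapy, TGCT surgery or death. A separate row gives AEs that start after other TGCT therapy and before any restart.
3. Report Treatment-Free PRO change from assessments up to that same date. Show later assessments separately, keeping those after other therapy apart from those after restart.
4. State in the text that the truncated figures are to be read beside the full-period figures, because other therapy may itself be a consequence of stopping pexidartinib.

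The cost is some wording, one date already derived for the primary endpoint, and an extra row or so per table. The downside is small numbers in the late rows. No extension to the Re-Treatment period or the Continuation Cohort is proposed.
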